7.4.2. Disease-Specific Concomitant Medications and Concomitant Medications

Concomitant medications are defined as medications taken on or after the first dose of study drug. Healthy Participants (Cohorts 1 to 4; and Cohort 8) will have a single summary of concomitant medications produced.

For the virally suppressed CHB population [participants in cohorts 5 to 7], separate displays will be provided for “disease-specific medications” (eg, medications recorded on the HBV Treatment eCRF) and for “other concomitant medications” (eg, medications recorded on the CM eCRF). Use of concomitant medications will be summarized by preferred name using the number and percentage of participants for each treatment group (active group within each cohort and all participants [within population] assigned to placebo). A participant reporting the same medication more than once will be counted only once when calculating the number and percentage of participants who received that medication. The summary will be ordered by descending overall frequency for preferred term. For preferred terms with the same frequency, sorting will be done alphabetically by preferred term.

For the purposes of analysis, any medications with a start date prior to or on the first dosing date of study drug that continued to be taken after the first dosing date, or medications started after the first dosing date of study drug will be considered to be concomitant medications.

Medications started and stopped on the same day as the first dosing date of study drug will also be considered concomitant. Medications with a stop date prior to the date of first dosing date of study drug will be excluded from the concomitant medication summary. If a partial stop date is

entered, any medication with the month and year (if day is missing) or year (if day and month are missing) prior to the date of first study drug administration will be excluded from the concomitant medication summary. Medications with completely missing start and stop dates will be included in the concomitant medication summary, unless otherwise specified. Summaries will be based on the Safety Analysis Set.

No formal statistical testing is planned.

All prior and concomitant medications (other than per-protocol study drugs [and HBV medications for virally suppressed CHB participants]) will be provided in by-participant listings for each participant population and be sorted by cohort, participant ID number, and administration date in chronological order.

7.5. Investigator Assessment of Electrocardiogram Results

A shift table of the investigators' assessment of ECG results at each postbaseline visit (Day 85, Day 141, and FU-WK24) compared with the baseline values will be presented separately by participant population. Displays will be by treatment group (active group within each cohort and all participants [within population] assigned to placebo) using the following categories: normal; abnormal, not clinically significant; abnormal, clinically significant; or missing. The number and percentage of participants in each cross-classification group of the shift table will be presented. Participants with a missing value at predose or postdose will not be included in the denominator for percentage calculation. No formal statistical testing is planned.

A by-participant listing for investigator ECG assessment results will be provided separately for each participant population. The listing will be sorted by cohort, participant ID, and date in chronological order.

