6.4.1. Electrocardiogram Assessment

Recording of the ECG will occur at screening ([Table 1](#), [Table 2](#), and [Table 3](#)).

Participants should rest quietly in the supine position for a minimum of 10 minutes prior to each scheduled 12-lead ECG acquisition and should remain in that position until the recording is complete.

The investigator or other qualified individual at the study center will review the ECG for abnormalities.

Collection of additional ECGs for routine safety monitoring at additional time points or days is at the discretion of the investigator based on GCP.

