6.6. Assessments for Early Discontinuation From Investigational Product or From the Study

If a participant discontinues dosing with the investigational product (see Section [3.3](#)), for example as a result of an AE, the ET visit evaluation and/or procedures outlined in [Table 1](#), [Table 2](#), and [Table 3](#) should be performed within 7 days of last investigational product dose. If the last investigational product dose was received more than 7 days prior to decision to discontinue future dosing, the ET visit should be completed at the next scheduled study visit. Every attempt should be made to keep the participant on the study and continue to perform study-related follow-up and procedures. Evaluations indicating abnormal results believed to be related to investigational product at the ET visit should be repeated weekly or as often as deemed appropriate by the investigator until the abnormality resolves, returns to baseline visit levels, or is otherwise explained.

If a participant withdraws consent from the study, the ET visit will be their last study visit.

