8.3.1.2. Safety

The Safety Analysis Set will include all randomized participants who received at least 1 dose of investigational product. Participants who received treatment other than that to which they were assigned will be analyzed according to the treatment received.

The Safety Analysis Set is the primary analysis set for safety analyses. All data collected during the study will be included in the safety summaries.

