Day 15	Day 15	Day 15 [#]	Day 15 [#]
Day 29	Day 29* ^{\$}	Day 29*# ^{\$}	Day 29*# ^{\$}
Day 43	–	Day 43	Day 43
Day 57	Day 57* ^{\$}	Day 57*# ^{\$}	Day 57*# ^{\$}
Day 71	FU-WK2	Day 71	Day 71
Day 85	FU-WK4^{\$}	Day 85*# ^{\$}	Day 85*# ^{\$}
Day 99	–	FU-WK2	Day 99
Day 113	–	FU-WK4*#^{\$}	Day 113*# ^{\$}
Day 127	–	–	Day 127
Day 141	FU-WK12^{\$}	–	Day 141*# ^{\$}
Day 155	–	–	FU-WK2
Day 169	–	FU-WK12*#^{\$}	FU-WK4*#^{\$}
Day 225	FU-WK24*^{\$}	–	FU-WK12*#^{\$}
Day 253	–	FU-WK24*#[#]	–
Day 309	–	–	FU-WK24*#[#]

*Creatinine Clearance (estimated using Cockcroft-Gault method) collected at this subset of visits.

#Viral biomarkers (HBV DNA, quantitative HBsAg, anti-HBsAg antibody, HBcrAg, HBeAg and anti-HBeAg antibody) collected at this subset of visits for participants in Cohorts 5, 6, and 7 (only).

\$ Antibody to HBsAg [Phase 1a participants only].

Table 3-2. Remapped Follow-Up Visits for Vital Signs, Weight, and BMI

Nominal Visit	Cohorts 1, 2	Cohorts 3, 4, 5, 6	Cohorts 7, 8
Last Value prior to first dose date=Baseline	Baseline*#	Baseline*#	Baseline*#
Day 8	Day 8	–	–
Day 15	Day 15	Day 15	Day 15
Day 29	Day 29	Day 29*#	Day 29*#
Day 43	–	Day 43	Day 43
Day 57	Day 57*#	Day 57*#	Day 57*#
Day 64	FU-WK1	–	–
Day 71	FU-WK2	Day 71	Day 71
Day 85	FU-WK4	Day 85*#	Day 85*#
Day 92	–	FU-WK1	–
Day 99	–	FU-WK2	Day 99
Day 113	–	FU-WK4	Day 113*#
Day 127	–	–	Day 127
Day 141	FU-WK12	–	Day 141*#
Day 148	–	–	FU-WK1
Day 155	–	–	FU-WK2
Day 169	–	FU-WK12	FU-WK4
Day 225	FU-WK24*	–	FU-WK12
Day 253	–	FU-WK24*	–
Day 309	–	–	FU-WK24*

*Weight (and the calculation of BMI) performed at this subset of the visits.

“Pre-dose” and “Post-dose” timepoints will be displayed for vital signs that were collected on injection days.

Table 3-3. Remapped Follow-Up Visits for IFNy ELISpot Assay

Nominal Visit	Cohorts 1, 2	Cohorts 3, 4, 5, 6	Cohorts 7, 8
Last Value prior to first dose date=Baseline	Baseline	Baseline	Baseline
Day 15	Day 15	Day 15	–
Day 29	Day 29	Day 29	–
Day 43	–	Day 43	–
Day 57	Day 57	Day 57	Day 57
Day 71	FU-WK2	Day 71	Day 71
Day 85	FU-WK4	Day 85	Day 85
Day 99	–	FU-WK2	Day 99
Day 113	–	FU-WK4	Day 113
Day 127	–	–	Day 127
Day 141	FU-WK12	–	Day 141
Day 155	–	–	FU-WK2
Day 169	–	FU-WK12	FU-WK4
Day 225	FU-WK24	–	FU-WK12

Table 3-4. Remapped Follow-Up Visits for ECGs

Nominal Visit	Cohorts 1, 2	Cohorts 3, 4, 5, 6	Cohorts 7, 8
Last Value prior to first dose date=Baseline	Baseline	Baseline	Baseline
Day 85	–	Day 85	Day 85
Day 141	–	–	Day 141
Day 225	FU-WK24	–	–
Day 253	–	FU-WK24	–
Day 309	–	–	FU-WK24

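### The only ECG table is a by-visit shift at three scheduled visits, with no worst-postbaseline row and no visible row for early-termination or unscheduled ECGs

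*SAP*

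**What the plan says.** SAP 7.5 specifies a single ECG table: a shift in the investigator's assessment of "ECG results at each postbaseline visit (Day 85, Day 141, and FU-WK24) compared with the baseline values". The categories are "normal; abnormal, not clinically significant; abnormal, clinically significant; or missing". On percentages it says: "Participants with a missing value at predose or postdose will not be included in the denominator for percentage calculation". The SAP's "Table 3-4. Remapped Follow-Up Visits for ECGs" lists the same visits: Day 85 for Cohorts 3 to 8, Day 141 for Cohorts 7 and 8, and FU-WK24, which is Day 225, 253 or 309 depending on the cohort. SAP 7.5 adds: "A by-participant listing for investigator ECG assessment results will be provided separately for each participant population". It states no visit restriction for that listing.

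The protocol foresees other ECGs. Its schedules of assessments (Tables 1 to 3) mark a 12-lead ECG in the ET column. Section 6.4.1 says: "Collection of additional ECGs for routine safety monitoring at additional time points or days is at the discretion of the investigator". Section 6.6 says: "If a participant withdraws consent from the study, the ET visit will be their last study visit".

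On what should be summarized, Protocol 8.3.1.2 says: "All data collected during the study will be included in the safety summaries". Protocol 8.5 likewise commits to summarizing safety data from first dose to study completion. Protocol 8.5.4 asks for ECG data by population, treatment group and visit. SAP 2.3 declares no departures from the protocol's analyses.

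**The concern.** A by-visit table describes the ECG status of participants who had a tracing at that visit. It does not show how many dosed participants ever had a clinically significant abnormal ECG. The SAP answers that kind of question for laboratory data but not for ECGs.

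Scheduled post-dose ECGs are few and mostly late. An ET tracing or an extra one may therefore be the only recording made soon after an injection in a first-in-human study. If an abnormal tracing of that kind has no row, the table can show no abnormal results for a group in which one was recorded. With 8 active participants per cohort, one participant is 12.5 percentage points.

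**Working it through.** The plan states no ECG figure to reproduce. The check compares the texts and then gives a small illustration.

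**1. Timing of the tabulated ECGs** (SAP Table 3-4)
- Cohorts 1 and 2: one postbaseline row, Day 225. That is 225 − 1 = 224 days after the first dose and 225 − 57 = 168 days (24 weeks) after the last.
- Cohorts 3 to 8: first row at Day 85, which is 85 − 1 = 84 days after the first dose. Day 85 is itself a dosing day in these cohorts.
- ET visit (Protocol 6.6): within 7 days of the last dose, or at the next scheduled visit if more than 7 days have passed when dosing is stopped. An ET tracing can thus fall well before the first tabulated row.

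**2. How the SAP treats other safety data**
- Laboratory grades (SAP 7.2.2.1 and 7.2.2.2): any time postbaseline, most severe grade, with participants who have at least one postbaseline value as denominator.
- Liver criteria (SAP 7.2.3): all postbaseline visits.
- ECG (SAP 7.5): three named visits and no summary across visits.

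**3. Would an unseen mapping rule close the gap?** Part of the text around SAP 3.8.2, just before the visit tables, was not in the supplied copy, and it may say how ET and unscheduled records are assigned. If ET records are mapped to a visit, an ET abnormality could appear in that row. In Cohorts 1 and 2, however, the only postbaseline row is FU-WK24, so an early ET tracing would be either unmapped or labelled as a week-24 follow-up result. An abnormal extra ECG that is normal by the next scheduled one still has no row of its own. No mapping rule produces a worst-value row.

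**4. Illustration.** Group sizes come from SAP 1.3: 8 active and 2 placebo per cohort. Placebo pooled by population gives 5 × 2 = 10 healthy and 3 × 2 = 6 CHB participants. The number of abnormal tracings, k, is assumed, because the documents give no rate. Suppose k participants leave the study and each has, as the only post-dose ECG, a clinically significant abnormal ET tracing that is not mapped. Everyone else attends with no such abnormality. The table then shows 0/(n − k) with k missing, while a worst-value row shows k/n. Exact (Clopper-Pearson) 95% intervals are in brackets for the active cohort.

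| Group | n | k | Table as planned | Worst-value row |
|---|---|---|---|---|
| Active cohort | 8 | 1 | 0/7 = 0% (0 to 41.0%) | 1/8 = 12.5% (0.3 to 52.7%) |
| Active cohort | 8 | 2 | 0/6 = 0% (0 to 45.9%) | 2/8 = 25.0% (3.2 to 65.1%) |
| Pooled healthy placebo | 10 | 1 | 0/9 = 0% | 1/10 = 10.0% |
| Pooled CHB placebo | 6 | 1 | 0/5 = 0% | 1/6 = 16.7% |

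If the participant stays on study, or has an abnormal extra ECG that later normalises, the scheduled rows show 0/8 where a worst-value row shows 1/8.

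**The case against.** The strongest reply is that SAP 7.5 does what Protocol 8.5.4 asks, a by-visit ECG summary, and that the protocol nowhere promises a worst-value row. That is correct. The all-data sentence is general and sits in the definition of the Safety Analysis Set. But a by-visit layout can stand beside a worst-value row, and Protocol 8.5 repeats the general commitment.

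Four further replies carry weight.
- **Participants with no ECG at a visit are not removed from the table.** Missing is a displayed category, and only the percentage denominator omits them. The 0/7 would appear with one participant visibly missing.
- **Stopping dosing is not leaving the study.** Protocol 4.1.1 and 6.6 ask for continued follow-up, so many who stop would still have a week-24 ECG. The 0/7 case needs study withdrawal.
- **The results have other routes.** The listing covers them, and with 8 active participants per cohort it can be read in full. Under Protocol 7.6, an abnormal ECG with signs or symptoms that meets the AE definition is recorded as an AE. This backstop is partial: that rule does not by itself compel an AE record for an asymptomatic reading.
- **The sparse schedule comes from the protocol.** A new row adds no early scheduled ECG.

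A reader might also infer that the SAP excludes the tracings most likely to be abnormal and so biases the table toward no ECG effect. The documents do not support that. They give no abnormality rates and describe the extra ECGs as routine safety monitoring. The same rule applies to active and placebo participants, and the mapping text is partly unseen. Both the exclusion and its direction are inferences.

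**Conclusion.** The point holds as a gap in one descriptive table. In the text available, SAP 7.5 and Table 3-4 give ECG shifts only at Day 85, Day 141 and FU-WK24, with no worst-postbaseline row and no visible place for ET or unscheduled tracings. A clinically significant abnormality on such a tracing could reach the reader only through the listing, or through the AE tables if it qualifies.

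For one assumed participant among 8 active, the difference is 0/7 with one missing, or 0/8, against 1/8 (12.5%). The 0/7 figure rests on study withdrawal and no mapping of the ET record. The 0/8 figure rests on a scheduled tracing without the abnormality and no row that takes the worse result.

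The documents do not show that the safety evaluation is biased or that these ECGs go unreported. The primary endpoint consists of TEAEs, SAEs and laboratory abnormalities, so ECG assessments are not part of it. This is a cheap improvement worth making.

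**What to change.** In SAP 7.5, keep the by-visit rows and add a shift row for the worst postbaseline assessment, using every post-dose ECG: scheduled, ET and unscheduled. The denominator should be Safety Analysis Set participants with a baseline and at least one post-dose ECG. Footnote how many participants in each group contributed unscheduled ECGs. In the same section or beside Table 3-4, state or cross-refer to how ET and unscheduled ECGs are assigned in the by-visit rows.

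The cost is a few lines of SAP text and one extra block in an existing table, with no new data, visits or procedures. The downside is uneven ascertainment: discretionary ECGs may raise detection more in one group than another. The footnote lets the reader judge that, and the by-visit rows remain as the evenly ascertained view.

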7.6. Other Safety Measures

A by-participant listing of subject pregnancies during the study will be provided.

No additional safety measures are specified in the protocol.

Although not necessarily related to safety, a by-participant listing of all comments received during the study on the comments eCRF will be provided.

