6.3.4. Participant Diaries for Reactogenicity

Participants will be asked to record potential investigational product reactions based on solicited events via a diary for 7 days following each administration of investigational product. Review of participant reactogenicity data will occur at the next visit that is greater than 7 days postdose ([Table 1](#), [Table 2](#), and [Table 3](#)). Solicited events will include, but may not be limited to, temperature, local events of injection-site pain, swelling, erythema, induration, and systemic events of fatigue, fever, arthralgia, myalgia, headache, and nausea. Any reactogenicity event that meets the criteria for AEs based on Section 7.1.1 must be reported in the appropriate eCRF.

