8. STATISTICAL CONSIDERATIONS

Details of the statistical methods will be provided in the statistical analysis plan and the biomarker analysis plan, including any deviations from the original statistical analyses planned.

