8.5.2. Adverse Events

The analysis of data on safety and reactogenicity events will be based on the Safety Analysis Set. Data from participants receiving PBO in different cohorts may be combined within the same population for the final analysis.

Clinical and laboratory AEs will be coded using the current version of the MedDRA. System organ class, high-level group term, high-level term, preferred term (PT), and lower-level term will be attached to the clinical database.

Events will be summarized on the basis of the date of onset for the event. A treatment-emergent AE will be defined as:

- Any AE that begins on or after the date of first dose of investigational product and through the duration of the study; or any AE leading to investigational product discontinuation.

Summaries (number and percentage of participants) of treatment-emergent AEs (by system organ class, high-level term, if applicable, and PT) will be provided by population and treatment group using the current version of MedDRA.

- All TEAEs
- TEAEs of Grade 3 or higher
- TEAEs of Grade 2 or higher
- All treatment-related TEAEs
- Treatment-related TEAEs of Grade 3 or higher
- Treatment-related TEAEs of Grade 2 or higher
- All treatment-emergent SAEs
- All treatment-related treatment-emergent SAEs
- All TEAEs leading to premature discontinuation of any investigational product
- All TEAEs leading to temporary interruption of any investigational product

All AEs collected during the study will be presented in the data listings.

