1.1. Study Objectives and Endpoints

Primary Objective	Primary Endpoint

 To evaluate the safety and tolerability of repeated dosing of GS-2829 and GS-6779 in healthy participants and in virally suppressed participants with CHB 	
 Proportion of participants with treatment-emergent AEs, SAEs, and laboratory abnormalities
Secondary Objective	Secondary Endpoints

 To evaluate the immunogenicity of repeated dosing of GS-2829 and GS-6779 in healthy participants and in virally suppressed participants with CHB 	
 Incidence and magnitude of vaccine-induced T-cell responses
Exploratory Objectives	Exploratory Endpoints

 To evaluate the impact of GS-2829 and GS-6779 on HBV-specific viral biomarkers in participants with CHB 	
 Change in HBsAg from baseline Proportion of participants with HBsAg loss with or without HBsAg seroconversion Changes in quantitative hepatitis B e antigen (HBeAg) from baseline

Note: Only exploratory objectives to be analyzed under this SAP are included. Exploratory objectives may be analyzed outside of this SAP will not be described here.

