1.2. Study Design

This is a randomized, blinded, placebo-controlled, Phase 1a and Phase 1b study to evaluate the safety, tolerability, and immunogenicity of repeated doses of GS-2829 and GS-6779 in healthy participants (Phase 1a) and participants with virally suppressed CHB (Phase 1b). The study will comprise 8 cohorts, which will enroll approximately 10 participants each, with a 4:1 randomization to either active viral vectors (GS-2829 and/or GS-6779) or Placebo (PBO).

The investigational products GS-2829 and GS-6779 are available as $\geq 1.0 \times 10^7$ FFU/mL. There are 2 doses in this study: high dose (0.5 mL of the undiluted solution) and low dose (0.5 mL of the 10-fold dilution of the high dose).

Phase 1a activities will be performed in healthy participants who are 18 to 60 years of age at a single study site in New Zealand (refer to protocol for complete inclusion and exclusion criteria).

Healthy participants will be enrolled into 1 of 5 cohorts to receive the investigational product as follows:

Cohort 1^{*} – Single low dose of GS-2829 or PBO on Day 1 and Day 57.

Cohort 2^{*} – Single low dose of GS-6779 or PBO on Day 1 and Day 57.

Cohort 3 – Single low dose of GS-2829 on Day 1 and Day 57; and single low dose of GS-6779 on Day 29 and Day 85 or PBO on Days 1, 29, 57, and 85.

Cohort 4 – Single high dose of GS-2829 on Day 1 and Day 57; single high dose of GS-6779 on Day 29 and Day 85 or PBO on Days 1, 29, 57, and 85.

Cohort 8 – Single high dose of GS-2829 on Day 1, Day 57, and Day 113; and single high dose of GS-6779 on Day 29, Day 85, and Day 141 or PBO on Days 1, 29, 57, 85, 113, and 141.

*Cohorts 1 and 2 will enroll concurrently and will receive investigational product in 2 groups, a sentinel group (2 active and 1 PBO, randomly assigned) and the remainder (6 active and 1 PBO), for a total of approximately 10 healthy participants per cohort. Dosing the remainder of Cohorts 1 and 2 and initiation of Cohort 3 will commence at the discretion of the investigator in consultation with the sponsor's medical monitor upon evaluation of available safety data through at least 14 days after the first dose of investigational product in Cohort 1 and 2 sentinel group participants.

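### The SAP plans no output from the solicited 7-day reactogenicity diary, so no planned table shows whether reactions change from one injection to the next

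*SAP*

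**What the plan says.** Protocol 6.3.4 sets up the diary: "Participants will be asked to record potential investigational product reactions based on solicited events via a diary for 7 days following each administration". The items are temperature, four injection-site signs and six systemic symptoms. The same section gives the route into the AE data: "Any reactogenicity event that meets the criteria for AEs based on Section 7.1.1 must be reported in the appropriate eCRF".

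Protocol 8.5.2 says: "The analysis of data on safety and reactogenicity events will be based on the Safety Analysis Set". It also permits pooled placebo: "Data from participants receiving PBO in different cohorts may be combined within the same population for the final analysis". Protocol Section 8 leaves the methods to later plans: "Details of the statistical methods will be provided in the statistical analysis plan and the biomarker analysis plan". SAP 6.1 assigns only the other exploratory biomarker endpoints to the biomarker plan, so the diary falls to the SAP.

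The SAP's primary endpoint is "Proportion of participants with treatment-emergent AEs, SAEs, and laboratory abnormalities". The diary appears in the SAP as a study procedure (1.2) and in the schedules and footnotes of Appendix 1. Section 7 contains no table, figure or listing of it, and 7.6 closes the safety section with "No additional safety measures are specified in the protocol".

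**The concern.** The primary objective is the safety and tolerability of repeated dosing, and Cohorts 7 and 8 exist to add a third dose of each vector. Whether local and systemic reactions grow, fade or stay level as injections accumulate is a natural question for this design. The diary is the instrument that records reactions in the same way after each injection. If the SAP is followed as written, those data are not summarised as solicited data, and the sentence in 7.6 gives the reader no sign that they exist.

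**Working it through.** **1. Where diary information could surface in the SAP**

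| Planned output | What it shows | What it does not show |
|---|---|---|
| TEAE tables (7.1.7.1) | Participants with AEs by SOC and PT; worst grade in the severity tables | Injection number; each participant counts once per summary |
| Injection-site and flu-like tables (7.1.8) | Coded AEs by treatment group and PT | Injection number; the solicited items as such |
| AEs related to each vector (7.1.3, 7.1.7.1) | Split by vector, resting on investigator attribution where both vectors are given (Cohorts 3 to 8) | First, second or third dose of that vector |
| Vital signs (7.3, Table 3-2) | Values before and 15 to 30 minutes after each injection, about 14 days after each dose, and about 7 days after some doses (both doses in Cohorts 1 and 2; the last dose elsewhere) | Reactions over the 7 days |
| AE listing and dosing listing (3, 4.2, 7.1.7.1) | Dates from which timing can be matched by hand | Any summary |

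Cohorts 1 and 2 separate the vectors by design, since each gives one vector only (for Cohort 1: "Single low dose of GS-2829 or PBO on Day 1 and Day 57"). They too have no table by injection.

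**2. Planned counts**

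The plan's own figure reproduces: 8 cohorts × 10 = 80 participants (64 active, 16 placebo). Injections per participant are 2 in Cohorts 1 and 2, 4 in Cohorts 3 to 6, and 6 in Cohorts 7 and 8.

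- Healthy: 10 × (2 + 2 + 4 + 4 + 6) = 180 diary periods.
- CHB: 10 × (4 + 4 + 6) = 140 diary periods.
- Total: 320.

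Placebo participants at injections 1 to 6, with 2 per cohort:

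- Healthy: 10, 10, 6, 6, 2, 2, which is 36 injections in 10 people, mean 3.6.
- CHB: 6, 6, 6, 6, 2, 2, which is 28 injections in 6 people, mean 4.7.

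**3. What a once-per-participant count hides**

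Assume independent reaction rates over four injections of 10, 20, 40 and 60%. The proportion ever reacting is 1 − 0.9 × 0.8 × 0.6 × 0.4 = 82.7%. Reverse the order to 60, 40, 20 and 10% and the answer is again 82.7%. Rising and falling reactogenicity give the same table entry.

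**4. Unequal injection counts: a caution only**

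Take no vaccine effect and an assumed, independent rate of 20% per injection. Then P(ever) = 1 − 0.8^k, which is 36.0, 59.0 and 73.8% for k = 2, 4 and 6. Pooled healthy placebo is (4 × 36.0 + 4 × 59.0 + 2 × 73.8)/10 = 52.8%. Cohort 8 minus placebo is 73.8 − 52.8 = 21.0 points, with a standard error of 21.7 (8 against 10 participants).

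| Assumed rate per injection | Gap (SE), independent | Gap (SE), within-person correlation 0.3 | Gap, correlation 0.9 |
|---|---|---|---|
| 10% | 16.1 (22.6) | 7.3 (20.7) | 0.7 |
| 20% | 21.0 (21.7) | 11.1 (23.4) | 1.2 |
| 30% | 19.8 (18.0) | 12.3 (22.6) | 1.5 |

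Gap over SE is 0.71 to 1.10 under independence and 0.35 to 0.54 at correlation 0.3. At 0.9 the gap is under a tenth of a standard error. The rates and correlations are assumptions; the documents give neither.

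**The case against.** Reactogenicity is not an endpoint at any level. The Protocol 8.5.2 sentence sits under adverse events and mainly fixes the analysis population. The summaries listed below it include no diary table and no split by injection. SAP 2.3, which declares no change from protocol-specified analyses, can therefore be read as accurate. The AE definition in Protocol 7.1.1 is broad, so many diary reactions should reach the AE tables, with severity and relatedness to each vector. Comparing Cohort 8 with Cohort 4 is meant to compare different numbers of doses, and SAP 4.2 tabulates those numbers. The documents do not say that diary entries are in the database or that the diary records a grade. In Cohorts 3 to 8 consecutive injections alternate vectors, so a plain trend over injections 1 to 6 would mix vector with dose number.

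Much of this stands. It limits the claim to the missing solicited-format and by-injection displays, and it shapes the remedy: severity only where recorded, vectors labelled, and a fallback on AE dates. It does not supply a table that shows change across injections. Nor does it rescue the 7.6 sentence, since the protocol specifies the diary and refers to analysing reactogenicity.

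**Conclusion.** The point holds and should be acted on. A safety instrument named in the protocol has no planned output, SAP 7.6 is wrong as worded, and no planned table can show whether reactions become more or less frequent or severe over repeated injections. Up to 320 diary periods lack a summary in solicited form. What that would change in the conclusions cannot be sized from the documents.

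A reader might infer three stronger things that the documents do not support:

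- **That reactions go unreported.** They do not: events meeting the AE definition are tabulated and listed, and those tables implement the primary endpoint correctly.
- **That the SAP drops an analysis the protocol spells out.** The protocol refers to reactogenicity analysis but lists no diary table.
- **That pooled placebo biases the comparison.** Pooling is permitted. Unequal injection counts (planned mean 3.6 in healthy and 4.7 in CHB placebo participants, against 2, 4 or 6 in active cohorts) call for care in reading ever-reacted percentages. The effect is of unknown size and may be near zero if the same people react each time.

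The count assumes full enrolment and complete dosing. The Safety Review Team charter, the biomarker analysis plan and a short stretch of SAP 3.8 ahead of the Table 3-1 rows were not available; the last is unlikely to hold a diary output.

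**What to change.** Keep the AE tables unchanged. Add:

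- **One descriptive table**, by population and treatment group: number and percentage of participants with each solicited event within 7 days after each injection number. Add maximum severity only if the diary records it, or take it from the matching AE.
- **Vector labels at each injection**, so that GS-2829 doses 1, 2 and 3 (injections 1, 3 and 5 in the alternating cohorts) are read against each other, and GS-6779 doses 1, 2 and 3 (injections 2, 4 and 6) likewise.
- **Denominator:** Safety Analysis Set participants who received that injection and have diary data for it. Show pooled placebo at the same injection number, with its n.
- **A by-participant diary listing.**
- **A corrected SAP 7.6** that names these outputs, with a note that ever-reacted percentages cover unequal numbers of injections.

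If diary entries are not in the database, build the table from AE onset and injection dates for the solicited terms and say so. That version covers only reactions reported as AEs.

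The cost is one table and one listing, with no testing and no new data collection. Cells are small (8 active per cohort; placebo n = 2 at injections 5 and 6), so the table is descriptive only.
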